procedures based on external tattoos and room lasers. A free- breathing trace of the Calypso transponders will be obtained to allow the patient to settle on the treatment table and to study real-time respiratory traces. The patient will then be asked to perform a therapist-coached modified slow vital capacity maneuver and DIBH maneuver [1] and hold their breath. Patients will have the ability to perform this maneuver with or without biofeedback from digital goggles that are placed over the patient's eyes and display the breathing trace of the Calypso transponders. The use of the digital goggles will be determined by patient preference or at the discretion of the treatment team. This will allow us to investigate whether real-time biofeedback adds to the reproducibility of patients holding their breath. A DIBH cone-beam CT will be acquired in approximately three breath-holds, once a week for standard fractionated RT patients or with each fraction for SBRT patients. After review and approval of the images, the patient will be treated while holding their breath using the DIBH maneuver. In standard fractionated RT patients the radiation treatment will be guided by the external tattoos and daily 2D kV imaging. The Calypso transponder signal will be used to monitor the level of the breath-hold during treatment. The breath-hold level based on the Calypso transponder signal will be verified daily by the 2D imaging and once a week in 3D by the DIBH cone-beam CT. In SBRT patients, the radiation treatment will be guided by the external tattoos and daily DIBH cone-beam CT. The Calypso transponder signal will be used to monitor the level of the breath-hold during treatment. The therapists will monitor the respiratory trace signal from the Calypso transponders throughout the treatment and will initiate the radiation treatment delivery when the patient holds his/her breath within the tolerance level the patient has been assigned to. This will be continued up until the initially planned 30 patients are accrued.. Should the transponder signal indicate that the target has moved outside of the preset tolerance, the therapists will hold further radiation treatment delivery until the patient's breathhold has returned to the desired target range or until the patient's setup has been corrected. In the additional 25 patients planned, the margins will be reduced in a step-wise fashion. The gate will be decreased 1mm per each set of 5 patients until the duty cycle (beam-on time) and number of DIBH attempts are doubled. The gate at which this occurs will be considered the minimum clinically feasible gate

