In the additional 25 patients to be accrued the window will be reduced in a step-wise fashion by 1mm for every 5 patients. Number of beam holds, treatment interruptions and total treatment time from first beam-on time to the last beam-off time will be recorded by the therapists.

If a patient cannot achieve the desired breath hold after 3 attempts and discussion with the therapist, the therapist can treat with the best breath-hold achievable and report the change in level to the treating physician. Additionally, the therapist will acquire an orthogonal pair of images. The physicist will then estimate the dosimetric effects per day in case the patient is still unable to achieve adequate breath hold the next day. Depending on the estimated dosimetry and the patient's reasons for not being able to achieve breath hold, the patient may be taken off protocol if unable to perform the breath hold to within +/- 5 mm for 3 consecutive treatment days. Patients who are taken off protocol prior to treatment completion will be treated based on the free-breathing treatment planning scan for the remainder of the radiation treatment course.

9.1 For patients undergoing SBRT in 10 or less fractions, the following procedures will be performed:

1. Standard setup procedures based on external tattoos will be performed.
2. The Calypso antenna will be deployed and positioned over the patient's chest. Tracking of the Calypso transponder signal will commence.

3. For patients who have been selected to use the digital goggles, the DIBH maneuver will be performed with visual biofeedback at least once a week and at least one fraction will be done without visual feedback. During treatment the radiation therapist will coach the patient on how to hold their breath during the treatment. On treatment days with visual feedback, the patient will be able to view and control his/her breathing through biofeedback using goggles (Myvu Personal Media Viewer, Myvu Corporation) or an iPhone that displays the Calypso trace. The couch position will be adjusted by the therapists in the treatment room to accurately set up the patient for treatment in DIBH based on the Calypso signal. The Calypso trace will be set to zero based on the DIBH level.
4. The patient will resume regular breathing and the therapists will leave the room.

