Reproducibility of using internal tumor surrogates (Calypso beacons) during repeated deep inspiration breath hold maneuvers with and without visual biofeedback will be evaluated by posthoc analysis of the Calypso signal traces. The ability to maintain the breathhold to within the tolerance level to which they have been assigned will be assessed. Number of beam holds and treatment interruptions will be recorded as an objective measure of the patient's ability to maintain their breathhold. Whether or not visual biofeedback will aid in the ability to hold their breath reliably and within the target region will be assessed using the number of treatment interruptions. We will also assess differences in duty cycle and number of DIBH attempts with and without visual biofeedback. Differences in the ability of maintaining the DIBH maneuver within the gate with and without visual biofeedback will be measured as duty cycle, a quantifiable measure of how long it takes to deliver a radiation treatment. It is related to how well patients can hold their breath and the tumor in the target position. Each patient will have the goggles 50% of the treatments and without goggles the other 50% of the time. Wilcoxon rank sum tests will be done to compare the duty cycle.

The residual intrafraction motion and drift during DIBH will be determined based on the Calypso signal traces which may provide critical insight into the ability to immobilize the tumor by DIBH. Beacon position stability will be determined on acquired cone-beam CTs by measuring the distance of the beacons to the center of the gross target volume {GTV} as well as the distance of the beacons to each other. Improvement of normal tissue dosimetry based on Calypso-guided DIBH will be determined from the treatment plans developed on the free-breathing and DIBH simulation CT scans. Specific dosimetric parameters will include the chest wall V30, total lung V20, mean lung dose, lung toxicity model metrics (Lyman model NTCP and parallel model fraction damaged (fdam)), mean and maximum esophageal dose, and maximum spinal cord dose.

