For the 1st secondary objective, we will compare the visual vs no visual biofeedback treatments (for patients who agree to use the digital goggles) by the number of treatment interruptions. We expect that there will be fewer treatment interruptions when using biofeedback. To this end Wilcoxon signed-rank tests will be conducted based on the patients who can successfully be treated.

For the 2nd secondary objective, we will assess differences in the ability of maintaining the DIBH maneuver within the fate with and without visual biofeedback. Such differences will be measured as duty cycle, and will be compared using Wilcoxon signed-rank tests based on the patients who can successfully be treated.

For the 3rd secondary objective, the residual intrafraction tumor motion (surrogated by Calypso) will be measured in all 3 dimensions and the euclidean distance will be calculated, which will then be correlated with the normal tissue dosimetry (see end of Section 12.0). Patients will receive multiple fractions and thus multiple measurements of such distance will be obtained from the same patients.

These repeated measures will be averaged for each patient and the correlation will be examined by simple linear regression. If such continuous data are skewed, we may either use an appropriate monotone transformation, or examine the nonparametric correlation coefficient (such as Spearman rank correlation coefficient) between the tumor motion and the normal tissue dosimetry instead.

For the 4th secondary objective, the potential increase in dose escalation and decrease in margins made possible by Calypso- guided DIBH, as contrasted to those obtained from the 40 CT scan, will be formulated as pair data from each patient and tested by using Wilcoxon signed-rank tests. Dosimetric parameters listed at the end of Section 12.0 will be used again for such analysis.

The 5th secondary objective does not require statistical analysis. See Section 12.0 for details.

For the 6th secondary objective, tumor shrinkage, beacon position and centroid changes in conventionally fractionated patients (totally 10), all measured as continuous variables, will be summarized descriptively.

For the 7th secondary objective, intra- and inter-fraction variation in lung volume preservation of multiple DIBH maneuvers will be recorded within each patient and summarized descriptively.

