15.2 Randomization

No randomization will occur in this study.

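### Section 12 names an unpaired test for a duty-cycle comparison made within patients, while section 14 names the paired test for the same endpoint

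*Combined protocol and SAP*

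**What the plan says.** Sections 12 and 14 both describe the comparison of duty cycle with and without visual biofeedback, which is the second secondary objective.

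- Section 12 sets a within-patient design: "Each patient will have the goggles 50% of the treatments and without goggles the other 50% of the time". It describes duty cycle as "a quantifiable measure of how long it takes to deliver a radiation treatment". The test follows: "Wilcoxon rank sum tests will be done to compare the duty cycle".
- Section 14 says of the same endpoint: "Such differences will be measured as duty cycle, and will be compared using Wilcoxon signed-rank tests".

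The first secondary objective compares the same two conditions, also by signed-rank test in section 14, "for patients who agree to use the digital goggles) by the number of treatment interruptions". Neither section gives a per-patient summary for either endpoint. Section 14 mentions averaging repeated measures within a patient only under the third secondary objective.

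On how often goggles are worn, sections 9.1 and 9.2 say that for selected patients the maneuver is "performed with visual biofeedback at least once a week and at least one fraction will be done without visual feedback".

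**The concern.** The rank-sum test assumes two independent samples. Here the two samples come from the same patients. Two analysts, one following section 12 and the other section 14, could report different p-values for one prespecified objective, and the choice between them could be made after the data are seen.

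The consequence also depends on something that neither section settles: whether each patient contributes one value per condition or every fraction enters separately. In the first case the rank-sum test tends to miss a real difference. In the second it can find one that is not there.

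**Working it through.** **1. Section 12 against section 14**

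| | Section 12 | Section 14 |
|---|---|---|
| Endpoint | Duty cycle, goggles vs none | Duty cycle, goggles vs none |
| Who provides data | Each patient, both conditions | Successfully treated patients |
| Test | Rank-sum (unpaired) | Signed-rank (paired) |
| Per-patient summary | Not given | Not given |

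Every patient in the comparison has both conditions, so the signed-rank test is the one that fits. This conclusion needs no assumed number.

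**2. Inputs for sizing**

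The plan has no figure to reproduce. It gives no alpha, effect size, correlation or number of goggle users for this comparison. Assumed: two-sided 5%, normal data, a shift of 0.5 SD and 25 patients. Section 14 expects at least 25 evaluable patients, but goggle use is optional, so the true number may be smaller.

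**3. One value per patient per condition**

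With SD σ and within-patient correlation ρ, the mean paired difference has variance 2σ²(1−ρ)/n. An unpaired test works as if it were 2σ²/n, which is too large by the factor 1/(1−ρ). The shift in units of the SD of the paired difference is 0.5/√(2(1−ρ)):

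- ρ = 0: 0.5/√2 = 0.35
- ρ = 0.3: 0.5/√1.4 = 0.42
- ρ = 0.5: 0.5/√1 = 0.50

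The paired test gains as ρ rises and the unpaired test does not. Simulation with 4,000 runs per cell and n = 25:

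| ρ | Null rejection, signed-rank | Null rejection, rank-sum | Power, signed-rank | Power, rank-sum |
|---|---|---|---|---|
| 0 | 4.6% | 4.5% | 38% | 40% |
| 0.3 | 4.4% | 1.9% | 51% | 37% |
| 0.5 | 4.4% | 0.9% | 64% | 35% |
| 0.7 | 4.8% | 0.0% | 85% | 32% |

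With 15 patients and ρ = 0.5, power is 43% against 17%. Repeat runs moved these figures by about two points.

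Positive correlation is plausible here. Section 12 narrows the tolerance window by 1 mm for every 5 extension patients and expects duty cycle to respond. Patients would then differ from one another by design, while one patient's two conditions should share a window.

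**4. Pooled fractions**

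Assumed: 25 patients with 4 or 30 fractions each, no true effect, intraclass correlation 0.3, 0.5 or 0.7, and 1,500 runs.

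- Half the fractions with goggles: the rank-sum test rejects 2.5%, 1.0% and 0.1% of the time.
- Goggle fractions drawn per patient, from about a fifth of the course to all but one: 19%, 27% and 35%. A separate run gave 22% to 38%.

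With unequal splits, patient differences no longer cancel between conditions, yet the test treats all fractions as independent.

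**5. Whether equal splits are assured**

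Section 3.1 cites 30 fractions. At an assumed 5 per week that is 30/5 = 6 weeks, so the section 9 minimums allow anything from 6 to 29 goggle fractions. A 15/15 split satisfies them, but so does 6/24. An odd-numbered course, for example an assumed 5 fractions, cannot be halved. The section 9 minimums are therefore compatible with section 12's 50% statement but do not enforce it.

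**The case against.** The strongest reply is that section 14 is the statistics section and already names the right test, so harm arises only if an analyst follows section 12 instead. These are secondary objectives, which section 4.1 says the trial will explore, with no stated power. That limits the weight of the point but does not remove it: the documents give no order of precedence between the two sections, and section 14 does not define the per-patient value that its own test needs.

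Two stronger readings are tempting, and the documents support neither.

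- A reader might infer that the interruption comparison is badly inflated because course totals would be compared across unequal numbers of fractions. No section says that totals will be compared. Section 14 contrasts treatments with and without biofeedback, and sections 9.1 and 9.2 record interruptions within the treatment steps, so a per-treatment reading is at least as natural. Section 12 also specifies a half-and-half split, at which even totals reject about 5% of the time under simulated equal rates. What remains is an undefined scale.
- A reader might infer that patients choose goggles day by day, from section 1: "The use of the digital goggles will be determined by patient preference or at the discretion of the treatment team". Sections 4.1, 5.0 and 14 refer to patients who agree to use the goggles, which supports reading this as whether a patient uses them at all. It remains true that "No randomization will occur in this study", so nothing randomizes which fractions are goggle fractions.

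**Conclusion.** The point holds as a direct contradiction on one secondary endpoint: the section 12 test does not fit the design that section 12 itself describes. The primary feasibility rule is not affected.

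The size is conditional. With one value per patient per condition, following section 12 costs nothing at zero correlation. Under the assumed 25 patients and 0.5 SD shift it costs about 14 points of power at correlation 0.3 (51 − 37) and about 29 at 0.5 (64 − 35). With pooled fractions and unequal splits the error runs the other way, to roughly 20% to 40% false rejection. All of these figures rest on assumed inputs. The mismatch of test and design does not.

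The missing scale for interruptions and the loosely matched goggle-use statements call for a minor clarification. They do not show a false-positive problem.

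**What to change.** 1. In section 12, replace the rank-sum test with the Wilcoxon signed-rank test.
2. In sections 12 and 14, state that duty cycle is summarized once per patient per condition, for example as the mean over that condition's fractions, and that the test is applied to the paired differences.
3. As a minor clarification, state in both sections that interruptions are analysed per fraction in each condition.
4. Reconcile the goggle-use statements in sections 1, 9.1, 9.2 and 12, including how an odd-numbered course is split and whether section 1 means use at all or use on a given day.

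The cost is one test name, two endpoint definitions and some wording. Therapists already record interruptions, so the only added item should be a note of goggle use for each fraction.

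There are limits. Rates from a condition with very few fractions are noisy, and a per-fraction rate does not remove bias from which days goggles are used.

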
The study will determine for the first time based on real-time tumor positioning information whether patients are able to reproducibly hold their breath in DIBH within excursions of 5.+-0.5cm or less. Furthermore, it will determine whether visual biofeedback improves the reproducibility of the breathhold. It will provide a unique dataset that will allow us to determine the concordance level of real-time tumor position information from the Calypso transponders, external surface signal and radiographic imaging. Ultimately, this study will allow us to quantify the decrease in radiation dose to organs at risk, decreased toxicity and amount of dose escalation made possible by the DIBH maneuver using real-time tumor position information.

Patients will be considered evaluable for protocol when they have had successful calypso beacon implantation without the beacons migrating> 5cm, and they have completed training in DIBH. In the extension of the protocol described below, 25 patients will be accrued; the expected time for completion of this study is 3 year from its approval.

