In a subsequent analysis of 7 patients undergoing over 250 treatments, we found that reproducibility was excellent as judged by spirometry and verification films using the diaphragm as a surrogate. Presumed respiration-dependent tumor motion was thus significantly reduced from $0.8 +/- 0.5\text{cm}$ to $0.02 +/- 0.14\text{ cm}$ (mean and standard deviation) compared to free breathing.[49] The main advantages observed with the use of DIBH were an increase in lung volume and motion of the PTV away from critical structures, e.g. spine. Thus, DIBH is an excellent tool to decrease target motion, decrease radiation dose to normal organs at risk and thus allow dose escalation to the tumor. DIBH treatments are currently clinically used in our department in appropriate patients. However, all DIBH treatments to date have relied on external or indirect markers as surrogates, sometimes combined with fluoroscopy or radiographic imaging for position verification. Given the potential pitfalls of external surrogates, we propose to investigate and improve DIBH treatment delivery using real-time tumor position information from implanted electromagnetic Calypso anchored transponders. In addition, the use of Calypso anchored transponders would simplify the DIBH maneuver to a single, comfortable breathhold, thus making it an attractive treatment option for a wider patient population.

Early studies in Switzerland and South Africa have shown the feasibility, stability and safety of bronchoscopic Calypso anchored transponder placement.[37] They have also demonstrated successful intrafraction motion detection.[22] An ongoing prospective international trial explores the safety and feasibility of endobronchial implantation of these electromagnetic fiducials. Interim results reported at ASTRO 2012 showed that 149 transponders were successfully implanted in 48 patients.[38, 51.] Two patients developed cough (G2), 1 patient

had dyspnea (G2) after bronchoscopy, two patients had pneumothoraces (G2), one patient had an anesthesia-related cardiac arrest (G4), and one patient had a lung infection (G3) concurrent with marker migration. One other patient experienced an asymptomatic migration of one transponder in a large airway that did not prevent localization and tracking by the Calypso system. Positional stability of these transponders is therefore 99% to date.

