9.0 TREATMENT/INTERVENTION PLAN

Using ENB and rEBUS, three Calypso transponders will be bronchoscopically placed within a small bronchial airway according to the Anchored Beacon Transponder Instructions for Use provided by Varian Medical (see section 20.0 Appendices). Two Calypso transponders will be permissible if it is technically not possible to place three transponders, as the tracking system works with a minimum of two transponders. Placement within 2 cm from the pleura should be avoided if possible to minimize the risk of pneumothorax. The position of the anchored transponders will be verified by fluoroscopy at the time of placement.

After a minimum of 3 days, the patient will be brought to the radiation simulation suite and immobilized using a custom-mademold, as per our standard protocol. Immobilization will be in a supine position unless prone treatment is required to meet the distance requirement

between the Calypso beacons and the Calypso detector plate. The patient will be coached through the DIBH maneuver and a breath-hold level that the patient can comfortably and reproducibly achieve using the Calypso system will be determined. A free-breathing (FB) 4D CT scan of the thorax and a CT scan in DIBH mode will be obtained using the RPM system. The patient's position and setup will be documented by tattoos and photographs.

Target volumes and normal structures will be delineated on the FB scan and on the DIBH scan. Target delineations will be performed on the registered 4DCT image set and on the DIBH scan as per current clinical practice. The Calypso beacons will also be delineated on each phase of the 4DCT study and on the DIBH scans.

Analysis of the 4DCT will provide an initial evaluation of the motion concordance between the Calypso beacon and the RPM external marker. Two radiation treatment plans will be developed, one based on the free-breathing scan and one based on the DIBH scan. These will be used for dosimetric comparison of treatment plans between a free-breathing and DIBH treatment. Only the DIBH treatment plan will be used clinically, unless a patient is unable to complete the DIBH maneuvers at the time of treatment. In that case, the plan based on the FB scan will serve as a backup plan. The beacon coordinates for the DIBH scan will be input to the Calypso system.

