12.0 CRITERIA FOR THERAPEUTIC RESPONSE/OUTCOME ASSESSMENT

Primary objectives:

- To evaluate the feasibility of Calypso transponders as an internal tumor surrogate to guide DIBH radiation treatments in real time.
- Feasibility is defined as completion of all treatments using the DIBH treatment plan and Calypso transponders. Patients who cannot have their transponders placed accurately bronchoscopically or for whom Calypso-guided DIBH will not be possible will be considered a failure. Patients who are removed from the protocol as a result of being unable to perform the breath hold for 3 consecutive treatment days at any point in the treatment course for reasons that are not related to the Calypso transponders, Calypso detection or complications of using the Calypso implantation or system (e.g. disease progression, severe side effects from treatment, e.g. esophagitis, infections, failure to thrive, generalized weakness, low blood counts etc.), will be replaced by new evaluable patients. Those patients will be treated with the free-breathing backup radiation treatment plan. The reason for the patient's inability to hold their breath will be recorded.

Secondary objectives:

- To compare the reproducibility with visual versus without visual biofeedback.
- To assess differences in the ability of maintaining the DIBH maneuver within the fate with and without visual biofeedback
- To measure the residual intrafraction tumor motion and associated improvement in normal tissue dosimetry during DIBH based on the Calypso lung transponder signal as a surrogate

- To measure the increase in dose escalation and the potential for decreasing margins made possible by Calypso-guided DIBH
- To determine the minimum clinically feasible gate margin for radiation
- To assess tumor shrinkage, beacon position and centroid changes in conventionally fractionated patients
- To assess intra- and inter-fraction variation in lung volume preservation of multiple DIBH maneuvers

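### The DIBH versus free-breathing plan comparison cannot credit a dosimetric gain to Calypso, and its metrics do not measure margin reduction

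*Combined protocol and SAP*

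**What the plan says.** Sections 2.0 and 12.0 give the fourth secondary objective as: "To measure the increase in dose escalation and the potential for decreasing margins made possible by Calypso-guided DIBH". The third pairs residual intrafraction motion with the associated improvement in normal-tissue dosimetry.

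Section 12.0 fixes how that improvement is obtained: "Improvement of normal tissue dosimetry based on Calypso-guided DIBH will be determined from the treatment plans developed on the free-breathing and DIBH" simulation CT scans. Its metrics are chest-wall V30, lung V20, mean lung dose, two lung-complication model outputs, and oesophageal and spinal-cord doses. For the fourth objective, Section 14.0 reuses these metrics in a paired Wilcoxon signed-rank test, with the Calypso-guided result "as contrasted to those obtained from the 40 CT scan" (the 4D CT; the extracted text shows the D as a zero).

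Section 9.0 describes the scans: "A free-breathing (FB) 4D CT scan of the thorax and a CT scan in DIBH mode will be obtained using the RPM system". It says of the two resulting plans: "These will be used for dosimetric comparison of treatment plans between a free-breathing and DIBH treatment". Section 4.2 states that enrolment does not alter the planning process.

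Section 1.0 promises more: "this study will allow us to quantify the decrease in radiation dose to organs at risk, decreased toxicity and amount of dose escalation".

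**The concern.** The objective names Calypso-guided DIBH as the source of the gain, but the contrast is between DIBH and free breathing. A clinician deciding whether to implant beacons needs to know what they add to DIBH performed without them. Section 3.2 says that alternative exists: "DIBH treatments are currently clinically used in our department in appropriate patients". It relies on external or indirect markers. The beacons require bronchoscopy under anaesthesia, which Section 5.0 acknowledges as an added risk compared with radiotherapy without fiducials.

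As the objective is worded, a significant signed-rank test could be read as evidence for the implant when it shows only that planning in deep inspiration spares more normal tissue than planning in free breathing. The margin half of the objective is where Calypso traces could contribute most, yet it is to be judged with dose metrics that contain no margin. The toxicity statement in Section 1.0 has no analysis behind it.

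**Working it through.** The documents give no sample size, power or effect size for the third or fourth secondary objective, so there is no stated figure to reproduce. The check concerns what the contrast can identify.

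**1. Parameters and conditions.** For one metric, let m be the mean under the free-breathing plan, d the effect of DIBH without Calypso, and k the increment from Calypso guidance. Let c = 1 if Calypso influences the DIBH scan and c = 0 if it does not.

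- Free-breathing plan: m
- DIBH plan: m + d + c·k
- Paired difference tested: d + c·k

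The design rows (intercept, DIBH, Calypso) are (1, 0, 0) and (1, 1, c). The rank is 2 for three parameters whether c is 0 or 1. With c = 1 only the sum d + k is estimable; with c = 0, k does not enter. A third plan representing the other Calypso state of DIBH gives rows (1, 0, 0), (1, 1, 0) and (1, 1, 1), of rank 3, and k becomes estimable.

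**2. Is c zero or one?** The documents conflict. Section 5.0 lists RPM on the simulator and Calypso tracking at the treatment machine. Section 9.0 has a comfortable, reproducible breath-hold level determined with the Calypso system at simulation, before the scans are described. The conclusion in step 1 holds either way.

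**3. What a significant test would mean.** Set k = 0 and simulate the paired signed-rank test (4,000 runs, two-sided 0.05, normal paired differences). The values of d are assumptions. The sample sizes match one and two of Section 14.0's sets of 25 evaluable patients; the number for this objective is not stated.

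| Assumed DIBH effect d (SD of paired difference) | Significant, n = 25 | Significant, n = 50 |
|---|---|---|
| 0 | 4.5% | 5.4% |
| 0.5 | 64.8% | 92.2% |
| 0.8 | 96.1% | about 100% |
| 1.0 | 99.7% | about 100% |

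The test works properly for d + c·k; significance says nothing about k.

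**4. Is a DIBH effect without beacons plausible?** Section 3.2 reports 30% less lung above 25 Gy with DIBH (5 patients). With spirometer-monitored DIBH (7 patients) it reports an increase from 69.4 to 87.9 Gy: 87.9 − 69.4 = 18.5 Gy, and 87.9 / 69.4 − 1 = 26.7%.

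**5. Margins.** None of the Section 12.0 metrics is a margin or a geometric uncertainty. All come from plans made under the unchanged planning process of Section 4.2, with no Calypso-specific planning margin stated. A difference in lung V20 between the two plans therefore cannot show how far a margin could be reduced.

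**6. Toxicity.** The study is nonrandomised and has no comparator group. Section 14.0 contains safety stopping rules but no comparative toxicity analysis. The nearest planned quantity is the model-based complication probability in Section 12.0.

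**The case against.** The strongest reply is that free breathing is the right comparator for the package. Section 3.1 says current DIBH is feasible in about 25% of lung radiotherapy patients because its breathing manoeuvre is hard, and expects Calypso to allow a simple inhalation and wider eligibility. For a patient who would otherwise be treated free breathing, DIBH with Calypso versus free breathing is the relevant question. This stands, and the contrast is valid under that description. It does not supply a Calypso-specific effect, and a paired comparison among patients already enrolled does not measure wider eligibility.

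A reader might answer that everyone enrolled could have had external-marker DIBH, having passed five 20-second breath-holds. The documents do not support that: Section 8.0 tests a comfortable inhalation and hold, not the harder manoeuvre described in Section 3.1. (Section 1.0 still describes the harder one at treatment; these passages also need reconciling.)

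The plan is also fairly open about the comparison. Section 9.0 names it correctly, Section 14.0 names the 4D CT, and Section 17.0 credits DIBH. No passage claims to separate the beacons from DIBH, so misreporting is a risk created by the objective's wording, not a certainty.

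Finally, these are exploratory secondary objectives in a feasibility study. The primary endpoint is unaffected.

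**Conclusion.** The concern holds as a matter of attribution. The planned test estimates DIBH as a package against free breathing, and the Calypso share cannot be recovered from it at any sample size. This covers the fourth secondary objective and the dosimetric-improvement part of the third. The margin part of the fourth is not measured by the listed metrics. The identification result needs no numerical assumption; the rejection rates of about 65% to over 99% at 25 patients depend on the assumed effects and normal differences.

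Three stronger readings are tempting but unsupported:

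- *The plan difference contains no Calypso information and would be the same without beacons.* Section 9.0 has Calypso helping to set the breath-hold level before the scans, so confounded is the defensible word, not absent.
- *The Section 3.2 series already show the whole gain without Calypso.* They include 5 and 7 patients, the dose series was spirometer-monitored and not RPM-based, and neither lung V25 nor achievable dose is a Section 12.0 metric. They show only that a sizeable gain without beacons is plausible.
- *The trial can say nothing about Calypso.* Residual motion and drift from the traces, beacon-to-RPM concordance and the stepwise reduction of the tolerance window are Calypso-specific. The third objective also correlates Calypso-measured motion with dosimetry, although that is not a contrast with and without Calypso.

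**What to change.** 1. In Sections 2.0, 12.0 and 14.0, restate this estimand as *DIBH versus free-breathing planning*, and add that it does not isolate the effect of Calypso guidance.
2. In Sections 12.0 and 14.0, assess margin potential from the Calypso residual-motion and drift data and the cone-beam CTs, not from the plan metrics.
3. Reconcile Sections 5.0 and 9.0 on whether Calypso is used at simulation.
4. In Section 1.0, replace the toxicity claim with the difference in model-predicted complication probability (NTCP).
5. Optional: an offline re-plan on the same DIBH scan, comparing external-marker margins with Calypso-supported margins. This is worthwhile only if the sponsor states both margins and their derivation. The documents give neither, and without a derivation the result would largely restate the margins assumed.

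Items 1, 3 and 4 are changes of text. Item 2 uses data already collected but needs a short analysis specification. Item 5 costs one offline plan per patient plus the margin derivation, with no added patient procedure. The price of the change is a claim less favourable to the device.
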